## 9.4. Other Safety Measures

Descriptive summaries of vital signs and change from baseline in vital signs will be presented by parameter, time point, and treatment category. Vital signs and physical examination results will each be listed by treatment, subject, and time point.

## **10.** CLINICAL MEASUREMENTS AND SYMPTOMS OF PNH

#### **10.1.1.** Clinical PNH Symptoms

The following clinical parameters will be summarized with counts and percentages by treatment category and study visit: fatigue, dyspnea, chest pain/discomfort, difficulty swallowing (esophageal pain, dysphagia), abdominal pain, headache, erectile dysfunction, hemoglobinuria, and jaundice.

#### **10.1.2.** Clinical Measurements of PNH

Continuous clinical measurements of PNH (LDH, hemoglobin, haptoglobin levels, absolute reticulocyte count, AST, total bilirubin, and direct bilirubin) will be summarized by summary statistics including change from baseline and percent change from baseline, by treatment category and study visit. Note that LDH, hemoglobin, haptoglobin, and absolute reticulocyte count that occur within a transfusion-impacted period will not be included in summaries but will be presented in respective listings. Categorical clinical measurements of PNH (number of blood transfusions, incidence of major thromboses) will be summarized with counts and percentages by treatment category (see Section 12.3 for a list of thrombosis events). Incidence of breakthrough hemolysis will be analyzed by the sponsor.

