13.6. Laboratory Assessments

Blood and urine samples will be obtained per the schedule of assessments in [Table 4](#). A list of the laboratory parameters measured is presented in [Table 5](#).

Samples will be collected into appropriate tubes, as specified by the clinical laboratory. All laboratory samples, with the exception of hemolysis testing at study drug discontinuation, will be analyzed by a central laboratory. Local laboratories may be used in place of the central laboratory at the investigator's discretion for logistical reasons (eg, such as delays in transport due to COVID-19), they may also be utilized for analysis of samples collected for assessment of possible AEs. Urine microscopy for samples collected at the investigative site will be performed at the site's local laboratory, where appropriate on-site testing capability exists (see [Section 13.6.1](#)). The additional renal and hepatic safety assessments may be performed at the investigative site or remotely at a location more convenient for the subject or via a home health service. If the use of a home health service is permitted, testing may be performed at the central laboratory or at a remote laboratory. The results from laboratory testing performed at a local or remote laboratory must be provided to the investigational site. Reference ranges for each local laboratory will be provided to the Sponsor and included in data listings. For out-of-range laboratory findings, the interpretation of clinically significant or not clinically significant should be denoted in the source records. Clinically significant laboratory findings in the opinion of the Investigator should be recorded as an AE and handled as described in [Section 13.9](#).

Table 5: Clinical Laboratory Evaluations

Chemistry	Coagulation	

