## 5.7.5. Fold Change from ULN (Fold x ULN)

Fold change from the upper limit of normal (ULN) (also known as the ratio to ULN, fold x ULN, or fold above the ULN) is calculated as (post-baseline result / ULN). If the ULN is missing, the fold x ULN is also set to missing.

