#### 5.7.12. Windowing and Multiple Lab Values

Unscheduled and early termination visits will be assigned to an analysis window according to the study day of the actual visit date using visit windows described in Table 3 below:

Visit	Relative Target Day	Analysis Visit Window
Screening (optional)	-35 to -1	Prior to Day 1
Day 1 (Baseline)	1	1
Week 4	29	2 to 43
Weeks 8 to 92	Week * 7 +1	Target Day -13 to Target Day +14
Week 96	673	660 to 701
Week 104 to 136	Week * 7 +1	Target Day -27 to Target Day +28
Week 144	1009	982 and later

Table 3:Visit Windows

For subjects with multiple lab values on the same day, special rules will be used to choose values eligible for display on tables and figures. For South African sites: on days with multiple test results, results from the local lab will be used. For other sites: on days with multiple test results, results from the central lab will be used. If there are still multiple records on the same date, then the median of available records on that date will be used; for these created median records, if applicable, the most frequent toxicity grade of the records used to calculate the median will be used.

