## 5.7.13.1. Transfusion-impacted Period for South Africa

The algorithm as defined below aims to exclude transfusion impacted lab measurements when possible, and acts to select local lab measurements over central lab measurements (for South Africa subjects) or central lab measurements over local lab measurements (for subjects outside of South Africa), when possible. This is due to a lack of reliable data obtained from the central lab in South Africa.

For South African sites, the algorithm for determining which values should be used in effectiveness analysis are as follows:

The Hb value to use for a particular visit is provided below. The first item matching the description in the list should be used.

- 1. Local lab value for Hb at the visit of interest closest to the target day.
  - a. If multiple results are equidistant from the target, use the latest.
  - b. If multiple records exist on the same day, find the median of the results on that day (for grading, set to the most frequent grade or worst grade if two grade have the same frequency).
- 2. Central lab value for Hb at the visit of interest closest to the target day.
  - a. If multiple results are equidistant from the target, use the latest.
  - b. If multiple records exist on the same day, find the median of the results on that day (for grading, set to the most frequent grade or worst grade if two grade have the same frequency).

If the value at the visit of interest was taken during a transfusion-impacted period:

- 3. Local lab pre-transfusion value that itself was not within 14 days after the subject received a pRBC or whole blood transfusion.
  - a. If multiple results are equidistant from the target, use the latest.
  - b. If multiple records exist on the same day, find the median of the results on that day (for grading, set to the most frequent grade or worst grade if two grade have the same frequency).
- 4. Central lab pre-transfusion value that itself was not within 14 days after the subject received a pRBC or whole blood transfusion.
  - a. If multiple results are equidistant from the target, use the latest.
  - b. If multiple records exist on the same day, find the median of the results on that day (for grading, set to the most frequent grade or worst grade if two grade have the same frequency).

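### LDH is summarized by visit only in reported units and percent change although laboratories with their own reference ranges are mixed; a multiple-of-ULN summary should be added beside it

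*SAP*

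**What the plan says.** **Scale.** SAP 10.1.2 states: "Continuous clinical measurements of PNH (LDH, hemoglobin, haptoglobin levels, absolute reticulocyte count, AST, total bilirubin, and direct bilirubin) will be summarized by summary statistics". The same sentence asks for change and percent change by treatment category and visit. Figures 14.4.3.2 to 14.4.3.4 plot the same three quantities. By-visit multiples of ULN are planned in SAP 9.2.2 for ALT, ALP, AST and bilirubin, and Table 14.3.3.12 covers liver tests only.

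**Laboratories.** Protocol 13.6 makes the central laboratory the default but adds: "Local laboratories may be used in place of the central laboratory", for logistical reasons at the investigator's discretion. Protocol 13.8 allows local tests when breakthrough hemolysis (BTH) is assessed. SAP 5.7.12 places unscheduled visits in analysis windows and then sets a same-day rule: "For South African sites: on days with multiple test results, results from the local lab will be used". Everywhere else the same-day preference is the central result. SAP 5.7.13.1 explains the South African preference: "This is due to a lack of reliable data obtained from the central lab in South Africa".

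**Reference ranges.** Protocol 13.6: "Reference ranges for each local laboratory will be provided to the Sponsor and included in data listings". SAP 5.7.5 defines the ratio to ULN, which "is calculated as (post-baseline result / ULN"), and so covers post-baseline values only.

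**Which parameters get a preferred laboratory.** SAP 5.6 (baseline) and SAP 5.7.13 (visit values) cover hemoglobin, reticulocytes, PNH RBC, the PNH RBC to WBC ratio, haptoglobin and FACIT-Fatigue. LDH is in neither list. SAP 10.1.2 nevertheless excludes LDH values from transfusion-impacted periods.

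**The concern.** LDH is a named secondary endpoint (SAP 3.2.2), and Protocol 5.5.2.2 uses it as the marker of intravascular hemolysis. The study has no control group (SAP 3.3), so change from baseline carries the effectiveness evidence and no concurrent arm would cancel a measurement artefact.

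The plan foresees laboratories with separate reference ranges but does not use those ranges in the by-visit LDH summaries. AST and total bilirubin, named in the same sentence as LDH, do get by-visit multiples of ULN elsewhere in the SAP.

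A subject's laboratory can differ between baseline and a later visit in at least three ways:

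- A visit has a single result from the non-preferred laboratory. The same-day rule then has nothing to choose between.
- An unscheduled local result, for example at suspected hemolysis, falls in the window.
- A direct-rollover subject carries a baseline from the prior study (Protocol 14.3.2).

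At stake is whether a movement in the LDH tables reflects hemolysis or the laboratory that ran the sample.

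**Working it through.** The documents give no figure to reproduce on this point: no LDH reference range, no count of laboratory switches and no sample-size calculation. The check compares the scales algebraically and then illustrates with assumed values.

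**Assumed inputs.** Laboratory A has ULN A = 250 U/L and laboratory B has ULN rA, with r from 0.8 to 2.0. True hemolysis is x multiples of ULN. Each ULN is assumed to track its assay's scale.

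**1. Subject switches from A to B with constant hemolysis.**

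- Raw change = xA(r − 1)
- Percent change = 100(r − 1)
- Change in multiple of ULN = x − x = 0

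With x = 1.5, baseline is 1.5 × 250 = 375 U/L:

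| r | Later value, U/L | Raw change, U/L | Percent change | Change in multiple of ULN |
|---|---|---|---|---|
| 0.80 | 300 | −75 | −20% | 0 |
| 0.88 | 330 | −45 | −12% | 0 |
| 1.14 | 427.5 | +52.5 | +14% | 0 |
| 1.25 | 468.75 | +93.75 | +25% | 0 |
| 1.50 | 562.5 | +187.5 | +50% | 0 |
| 2.00 | 750 | +375 | +100% | 0 |

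**2. Two subjects, no switch, same true fall from 2.0 to 1.2 × ULN.** At A: 500 to 300 U/L, which is −200 U/L and −40%. At B with r = 1.5 (ULN 375): 750 to 450 U/L, which is −300 U/L and −40%. In multiples of ULN both fall by 0.8. So raw change depends on the laboratory even without a switch, and percent change does not.

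**3. Effect on a group mean.** If a share s of subjects has switched, the mean percent change moves by 100·s·(r − 1) points:

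- s = 5%, r = 1.25: 100 × 0.05 × 0.25 = 1.25 points
- s = 10%, r = 1.5: 100 × 0.10 × 0.5 = 5 points
- s = 25%, r = 1.5: 100 × 0.25 × 0.5 = 12.5 points

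**4. If the ULN does not track the assay.** Suppose both assays agree but B quotes a ULN 1.25 times that of A. A constant 375 U/L is 375/250 = 1.5 × ULN at A and 375/312.5 = 1.2 × ULN at B. The ratio now shows a false fall of 0.3, while U/L correctly shows none.

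**The case against.** The best defence is that percent change is already planned and, as step 2 shows, cancels any stable difference between laboratories. A reader might infer that LDH results will follow country rather than drug effect, because South African sites favour local laboratories. The documents do not support that for percent change: a subject who stays with one laboratory is unaffected.

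The false within-subject change needs a switch. Central analysis is the default, and local substitution is for logistics, adverse-event assessment or hemolysis checks. Nothing shows how often it happens. A reader could also choose distant ULNs, say 250 and 480 U/L, and obtain 480/250 − 1 = +92%. Those ULNs are not in the documents, and that figure should not be read as an expected error.

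The threshold uses of LDH are already scaled: 1.5 × ULN in SAP Table 5 and 2 × ULN in the BTH definition (Protocol 14.3.6). Durability of response rests on hemoglobin (SAP 8.1.1). The summaries are descriptive, and no decision rule uses the by-visit LDH mean.

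All of this limits the size of the problem. It does not remove it. Raw values and raw changes are planned too, and they mix scales without any switch. Percent change is open to a switch. LDH also lacks the laboratory-selection rules that protect its companion measures. If the SAP 5.7.13 algorithm was meant to govern LDH, as the transfusion exclusion in SAP 10.1.2 suggests, switching would be limited, but the parameter list in 5.7.13 does not say so.

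**Conclusion.** The point holds as a low-cost improvement to a descriptive secondary analysis. By-visit raw LDH and raw change mix laboratory scales. Percent change is robust to stable laboratory differences but carries a false change of 100(r − 1) for each subject whose laboratory changes: −12% to +25% for r between 0.88 and 1.25. At group level this is 1.25 points with 5% switching at r = 1.25, and 12.5 points with 25% switching at r = 1.5. The values of r and the switching shares are assumptions, and zero artefact on the ratio scale assumes that each ULN tracks its assay.

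A reader might go further and infer that LDH should be reported only as a multiple of ULN. Step 4 is the reason not to: where ULNs differ for reasons other than assay scale, reported units are the better measure. The two belong side by side. The hematological response categories and the BTH definition are not affected in this way.

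**What to change.** - **Add the ratio.** In SAP 10.1.2, Table 14.4.1.3 and Figures 14.4.3.2 to 14.4.3.4, add LDH as a multiple of the ULN of the laboratory that ran the sample, as value and change. State that the SAP 5.7.5 ratio is also applied to the baseline value, using the range of the laboratory that produced it.
- **Keep the planned summaries.** Leave LDH in reported units, with change and percent change, in the same tables.
- **Apply the preferred-laboratory rule.** Name LDH in the laboratory-selection rules of SAP 5.6 (baseline) and SAP 5.7.13 (visit values). At the same time, reconcile the transfusion exclusion for LDH in SAP 10.1.2 with the parameter list in 5.7.13, which omits it.

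The cost is SAP wording, one more display and modest programming. The ratio is already needed for SAP Table 5 and reference ranges are already collected, so no new data are required. The remaining limitation is that the ratio removes the artefact only as far as each ULN tracks its assay scale.

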## 11. CLINICAL PHARMACOLOGY DATA ANALYSES

## 11.1. Pharmacokinetic Analyses

Sparse plasma and spot urine samples for determination of BCX9930 concentrations are planned to be collected at each study visit to the investigative site and 48 hours after evidence of BTH.

Plasma and urine concentrations of BCX9930 and BCX13559—a metabolite of BCX9930—will be listed with the time of sample collection and time of prior dose along with other available information. Any analysis of PK data including the calculation and assessment of PK parameters will be performed under a separate analysis plan.

## 11.2. Pharmacodynamic Analyses

In this study, PD assessments include PNH clone size (RBC and WBC), Factor Bb, serum AP activity as assessed by AP Wieslab, and additional exploratory assays.

Descriptive summaries of the above assessments including change from baseline will be presented by treatment category, dose regimen, and study visit. AP Wieslab (and other similar assays, if applicable) will be reported only as percent of baseline, not as actual value or percent change from baseline. Data values will be listed.

If PD assessments are reported with inequalities ( $<, \leq, >, \text{ or } \ge$ ), the same conventions used for laboratory values as described in Section 9.2 will be used.

Any further analysis of PD data including the relationship to PK concentrations will be performed under a separate analysis plan.

## **12. ATTACHMENTS**

## **12.1.** Table of Contents for Data Display Specifications

This table of contents provides the expected titles and numbers of the tables, listings, and figures of the final report. Changes to titles or numbering in the final report, additional data listings supporting the tables, or displays being split into multiple smaller displays for clarity will not necessitate a revision to the SAP, nor will they be considered a deviation from planned analyses.

Table Number	Title	Population
	Subject Dispesition	A 11
14.1.1	Analyzia Depulationa	All
14.1.2	Analysis Fopulations	
14.1.3.1	Demographic and Baseline Characteristics	MIII Safata
14.1.3.2	Demographic and Baseline Characteristics	Safety
14.1.4.1	Prior Medication	Safety
14.1.4.2	Concomitant Medication	Safety
14.1.5	I reatment Exposure and Compliance	Safety
14.2.1	Durability of Response – Hemoglobin (g/dL)	mlll
14.2.2.1	Hematological Response	mlTT
14.2.3	Functional Assessment of Chronic Illness Therapy (FACIT) Fatigue Scale	mITT
14.2.4	Total Time on Dose Level	mITT
14.2.5	Disease Severity	mITT
14.3.1	Overall Summary of Treatment-emergent Adverse Events	Safety
14.3.2.1	Treatment-emergent Adverse Events by MedDRA System Organ Class and Preferred Term	Safety
14.3.2.2	Treatment-emergent Adverse Events by MedDRA System Organ Class, Preferred Term, and Severity	Safety
14.3.2.3	Serious Treatment-emergent Adverse Events by MedDRA System Organ Class and Preferred Term	Safety
14.3.2.4	Treatment-emergent Adverse Events Related to Study Drug by MedDRA System Organ Class and Preferred Term	Safety
14.3.2.5	Grade 3 or 4 Treatment-emergent Adverse Events by MedDRA System Organ Class and Preferred Term	Safety
14.3.2.6	Treatment-emergent Adverse Events Leading to Treatment Discontinuation by MedDRA System Organ Class and Preferred Term	Safety
14.3.2.7	Treatment-emergent Adverse Events Leading to Treatment Interruption by MedDRA System Organ Class and Preferred Term	Safety
14.3.2.8	Treatment-emergent Major Adverse Vascular Events (MAVEs) by MedDRA System Organ Class and Preferred Term	Safety
14.3.2.9	Treatment-emergent Events of Special Interest (EOSIs) by MedDRA System Organ Class and Preferred Term	Safety
14.3.2.10.1	Time to First Dose Reduction – Kaplan-Meier	Safety
14.3.2.11.1	Time to Discontinuation Due to a Treatment-Emergent Adverse Event – Kaplan-Meier	Safety

Table 7:Data Displays

14.3.2.12.2	Kaplan-Meier Plot of First Drug-Related Rash	Safety
1422122	Kaplan Mejer Plot of First SARS-CoV-2 Infection	Safety

#### CONFIDENTIAL

14.3.2.13.4	Kaplan-Meier Plot of Duration of SARS-CoV-2 Infection	Safety
14.3.2.14.2	Kaplan-Meier Plot of First Potential Drug-Induced Liver Injury (pDILI) Event	Safety
14.3.2.15.2	Kaplan-Meier Plot of First Increase in Serum Creatinine > ULN	Safety
14.3.3.1.2	Distribution of Cholesterol and Triglycerides over Time	Safety
14.3.3.1.3	Selected Laboratory Parameters by Time	Safety
14.3.3.14.2	Hy's Law Plot of Maximum Total Bilirubin vs.	Safety
	Maximum ALT	-
14.3.3.14.3	Liver Test Safety Panel over Time, Baseline vs. On- study	Safety
14.3.3.14.4	Individual Patient Profile of ALT ALP AST	Safety:
	Hemoglobin and Total Bilirubin	Subjects with
	(Nate to an error dianter ALT ALD ACT and	Treatment-
	(Note to programmers: display AL1, ALP, AS1, and total bilimibin as the fold y ULN on a somi log avis (left	Emergent
	hand y axis) Display hemoglohin on a linear scale using	Grade 3 or 4
	the right-hand axis and display lines and symbols in red)	ALT, ALP,
	the right hand axis and display lines and symbols in rea/	ASI, or I otal
1422145	Distribution of Liver Toots over Times ALT AST ALD	Bilirubin
14.3.3.14.5	and Bilirubin	Safety
14.4.3.2	Plot of Clinical Measurements of PNH	mITT
	(Note to programmers: display LDH, hemoglobin,	
	haptoglobin, absolute reticulocyte count, AST, total	
	bilirubin, and direct bilirubin on the same plot if	
	possible. Display hemoglobin on a linear scale (on each	
	page, if multiple pages are needed) using the right-hand	
14422	axis and display lines and symbols in red.)	ITT
14.4.3.3	Plot of Clinical Measurements of PNH Change from	mili
	Dasenne	
	(Note to programmers: display LDH, hemoglohin	
	haptoglobin absolute reticulocyte count AST total	
	bilirubin, and direct bilirubin on the same plot if	
	possible. Display hemoglobin on a linear scale (on each	
	page, if multiple pages are needed) using the right-hand	
	axis and display lines and symbols in red.)	
14.4.3.4	Plot of Clinical Measurements of PNH Percent Change	mITT
	from Baseline	
	(Note to programmers: display LDH, hemoglobin,	
	naplogiopin, absolute reticulocyte count, AS1, total	
	possible. Display hemoglobin on a linear scale (on cach	
	possible. Display hemoglobili on a inical scale (on each page if multiple pages are needed) using the right hand	
	axis and display lines and symbols in red.)	
Listing	Title	Population
Number		-
16.2.1.1	Informed Consent	All
16.2.1.2	Subject Registry	
16.2.1.3	Subject Disposition	All
16.2.2	Protocol Deviations	All
16.2.3	Analysis Populations	All

## CONFIDENTIAL

16.2.4.1	Demographic and Baseline Characteristics	All
16.2.4.2	Medical History	All
16.2.4.3	Prior and Concomitant Medications	All
16.2.5.1	Study Drug Accountability	Safety
16.2.5.2	Overall Compliance	Safety
16.2.6.1	PNH Characteristics and Symptoms	All
16.2.6.2	Clinical Measurements of PNH	All
16.2.7	QLQ-AA/PNH Individual Question Responses	All
16.2.8.1	FACIT-Fatigue Scale Individual Question Responses	All
16.2.8.2	FACIT-Fatigue Scale Score	All
16.2.9	TSQM Individual Question Responses	All
16.2.10.1	Hemolysis Monitoring	All
16.2.10.2	Renal Events	All
16.2.10.3	Transfusions	All
16.2.11.1	Adverse Events	All
16.2.11.2	Serious Adverse Events	All
16.2.11.3	Adverse Events Leading to Study Discontinuation	All
16.2.11.4	Adverse Events Related to Study Drug	All
16.2.11.5	Adverse Events with Grade 3 or Grade 4 Severity	All
16.2.11.6	Major Adverse Vascular Events (MAVEs)	All
16.2.11.7	Events of Special Interest (EOSIs)	All
16.2.11.8	Hemolysis Adverse Events	All
16.2.11.9	Rash-related Adverse Events	All
16.2.11.10	Acute Kidney Injuries	All
16.2.12	Cutaneous Eruption Assessments	All
16.2.13.1	Laboratory Results - Clinical Chemistry	All
16.2.13.2	Laboratory Results - Hematology	All
16.2.13.3	Laboratory Results - Coagulation	All
16.2.13.4	Laboratory Results - Urinalysis	All
16.2.13.5	Laboratory Results - Other Laboratory Tests	All
16.2.14	Bedside 12-lead Electrocardiogram	All
16.2.15	Vital Signs, Height, and Weight	All
16.2.16	Physical Examinations	All
16.2.17.1	Plasma BCX9930 Pharmacokinetic Concentrations	All
16.2.17.2	Urine BCX9930 Pharmacokinetic Concentrations	All
16.2.18.1	Plasma BCX13559 Pharmacokinetic Concentrations	All
16.2.18.2	Urine BCX13559 Pharmacokinetic Concentrations	All
16.2.19	Individual PD Assessments and Biomarkers	All

## 12.2. Data Display Specifications

Specifications for data displays will be provided in a separate document.

12.3.	Preferred Terms that Qualif	y as MAVEs and Thrombotic Events
-------	-----------------------------	----------------------------------

MAVE Term	РТ	SOC	Thrombotic Event?
deep vein	Deep vein thrombosis	Vascular disorders	YES
thombosis	Deep vein thrombosis postoperative	Injury, poisoning and procedural complications	YES
	Deep vein thrombosis postoperative	Vascular disorders	YES
	Pelvic venous thrombosis	Vascular disorders	YES
pulmonary embolus	Pulmonary embolism	Respiratory, thoracic and mediastinal disorders	YES
	Pulmonary embolism	Vascular disorders	YES
myocardial infarction	Myocardial infarction	Cardiac disorders	YES
	Myocardial infarction	Vascular disorders	YES
	Acute myocardial infarction	Cardiac disorders	YES
	Acute myocardial infarction	Vascular disorders	YES
	ECG signs of myocardial infarction	Investigations	NO
	Periprocedural myocardial infarction	Injury, poisoning and procedural complications	YES
	Periprocedural myocardial infarction	Cardiac disorders	YES
	Dressler's syndrome	Cardiac disorders	NO
	Dressler's syndrome	Immune system disorders	NO
	Dressler's syndrome	Respiratory, thoracic and mediastinal disorders	NO
	Post procedural myocardial infarction	Injury, poisoning and procedural complications	YES

MAVE Term	PT	SOC	Thrombotic Event?
	Post procedural myocardial infarction	Cardiac disorders	YES
	Silent myocardial infarction	Cardiac disorders	YES
	Silent myocardial infarction	Vascular disorders	YES
transient ischemic	Transient ischaemic attack	Nervous system disorders	YES
аттаск	Transient ischaemic attack	Vascular disorders	YES
unstable angina	Angina unstable	Cardiac disorders	YES
	Angina unstable	Vascular disorders	YES
renal vein	Renal vein thrombosis	Renal and urinary disorders	YES
thrombosis	Renal vein thrombosis	Vascular disorders	YES
	Renal vein embolism	Renal and urinary disorders	YES
	Renal vein embolism	Vascular disorders	YES
acute peripheral	Vascular occlusion	Vascular disorders	YES
vascular occlusion	Cerebral vascular occlusion	Nervous system disorders	YES
	Cerebral vascular occlusion	Vascular disorders	YES
	Coronary vascular graft occlusion	Injury, poisoning and procedural complications	YES
	Coronary vascular graft occlusion	Cardiac disorders	YES
	Coronary vascular graft occlusion	Vascular disorders	YES
	Mesenteric vascular occlusion	Gastrointestinal disorders	YES

MAVE Term	РТ	SOC	Thrombotic Event?
	Mesenteric vascular occlusion	Vascular disorders	YES
	Retinal vascular occlusion	Eye disorders	YES
	Retinal vascular occlusion	Vascular disorders	YES
	Vascular access site occlusion	Injury, poisoning and procedural complications	YES
	Vascular access site occlusion	Vascular disorders	YES
	Vascular access site occlusion	General disorders and administration site conditions	YES
	Vascular device occlusion	General disorders and administration site conditions	NO
	Vascular device occlusion	Vascular disorders	YES
	Vascular graft occlusion	Injury, poisoning and procedural complications	NO
	Vascular graft occlusion	Vascular disorders	YES
	Vascular stent occlusion	General disorders and administration site conditions	YES
	Vascular stent occlusion	Vascular disorders	YES
mesenteric/visceral vein thrombosis or infarction	Mesenteric vein thrombosis	Gastrointestinal disorders	YES
	Mesenteric vein thrombosis	Vascular disorders	YES
	Portosplenomesenteric venous thrombosis	Hepatobiliary disorders	YES

MAVE Term	РТ	SOC	Thrombotic Event?
	Portosplenomesenteric venous thrombosis	Gastrointestinal disorders	YES
	Portosplenomesenteric venous thrombosis	Vascular disorders	YES
	Intestinal infarction	Gastrointestinal disorders	YES
	Intestinal infarction	Vascular disorders	YES
	Visceral venous thrombosis	Gastrointestinal disorders	YES
	Visceral venous thrombosis	Vascular disorders	YES
mesenteric/visceral	Mesenteric artery thrombosis	Gastrointestinal disorders	YES
or infarction	Mesenteric artery thrombosis	Vascular disorders	YES
	Intestinal infarction	Gastrointestinal disorders	YES
	Intestinal infarction	Vascular disorders	YES
hepatic/portal vein	Budd-Chiari syndrome	Hepatobiliary disorders	YES
chiari syndrome)	Budd-Chiari syndrome	Vascular disorders	YES
cerebral arterial	Cerebral artery occlusion	Nervous system disorders	YES
occlusion/cerebrovas cular accident	Cerebral artery occlusion	Vascular disorders	YES
	Intraoperative cerebral artery occlusion	Injury, poisoning and procedural complications	YES
	Intraoperative cerebral artery occlusion	Nervous system disorders	YES
	Intraoperative cerebral artery occlusion	Vascular disorders	YES

MAVE Term	РТ	SOC	Thrombotic Event?
	Precerebral artery occlusion	Nervous system disorders	YES
	Precerebral artery occlusion	Vascular disorders	YES
	Cerebrovascular accident	Nervous system disorders	YES
	Cerebrovascular accident	Vascular disorders	YES
	Cerebrovascular accident prophylaxis	Surgical and medical procedures	NO
cerebral venous	Cerebral venous thrombosis	Nervous system disorders	YES
occlusion	Cerebral venous thrombosis	Vascular disorders	YES
renal arterial thrombosis	Renal artery thrombosis	Renal and urinary disorders	YES
	Renal artery thrombosis	Vascular disorders	YES
gangrene (nontraumatic; nondiabetic)	Gangrene	Infections and infestations	NO
	Gangrene	Vascular disorders	YES
	Gangrene	Skin and subcutaneous tissue disorders	NO
	Arteriosclerotic gangrene	Infections and infestations	YES
	Arteriosclerotic gangrene	Vascular disorders	YES
	Arteriosclerotic gangrene	Skin and subcutaneous tissue disorders	YES
	Peripheral arterial occlusive disease	Vascular disorders	YES
	Femoral hernia gangrenous	Infections and infestations	NO
	Femoral hernia gangrenous	Gastrointestinal disorders	NO

MAVE Term	PT	SOC	Thrombotic Event?
	Femoral hernia gangrenous	Vascular disorders	YES
	Inguinal hernia gangrenous	Infections and infestations	NO
	Inguinal hernia gangrenous	Vascular disorders	YES
	Inguinal hernia gangrenous	Gastrointestinal disorders	NO
	Dry gangrene	Vascular disorders	YES
	Dry gangrene	Skin and subcutaneous tissue disorders	NO
	Gas gangrene	Infections and infestations	NO
	Gas gangrene	Vascular disorders	YES
	Gas gangrene	Skin and subcutaneous tissue disorders	NO
	Fournier's gangrene	Infections and infestations	NO
	Fournier's gangrene	Musculoskeletal and connective tissue disorders	NO
	Fournier's gangrene	Reproductive system and breast disorders	NO
	Penile gangrene	Infections and infestations	NO
	Penile gangrene	Reproductive system and breast disorders	NO
	Penile gangrene	Vascular disorders	YES
	Scrotal gangrene	Infections and infestations	NO
	Scrotal gangrene	Vascular disorders	YES
	Scrotal gangrene	Reproductive system and breast disorders	NO

MAVE Term	PT	SOC	Thrombotic Event?
	Scrotal gangrene	Skin and subcutaneous tissue disorders	NO
	Umbilical hernia gangrenous	Infections and infestations	NO
	Umbilical hernia gangrenous	Vascular disorders	YES
	Umbilical hernia gangrenous	Gastrointestinal disorders	NO
	Abdominal hernia gangrenous	Infections and infestations	NO
	Abdominal hernia gangrenous	Gastrointestinal disorders	NO
	Incisional hernia gangrenous	Infections and infestations	NO
	Incisional hernia gangrenous	Vascular disorders	YES
	Incisional hernia gangrenous	Gastrointestinal disorders	NO
amputation (nontraumatic; nondiabetic)	Amputation	Surgical and medical procedures	NO
	Hemipelvectomy	Surgical and medical procedures	NO
	Leg amputation	Surgical and medical procedures	NO
	Amputation of penis	Surgical and medical procedures	NO
	Arm amputation	Surgical and medical procedures	NO
	Foot amputation	Surgical and medical procedures	NO
	Cervix colporrhaphy with amputation	Surgical and medical procedures	NO
	Finger amputation	Surgical and medical procedures	NO
	Interscapulothoracic amputation	Surgical and medical procedures	NO

MAVE Term	PT SOC		Thrombotic
			Event?
	Hand amputation	Surgical and medical procedures	NO
	Limb amputation	Surgical and medical procedures	NO
	Spontaneous amputation	Vascular disorders	NO
	Spontaneous amputation	Skin and subcutaneous tissue disorders	NO
	Toe amputation	Surgical and medical procedures	NO
dermal thrombosis	Thrombophlebitis superficial	Vascular disorders	YES
	Vascular skin disorder	Skin and subcutaneous tissue disorders	NO
	Vascular skin disorder	Vascular disorders	YES

